**Reason for the amendment**

To incorporate FDA's request for the SYM 2014-02 study to tabulate TEAE incidence by subject Fitzpatrick Skin Type (individual type, pooled I-IV vs. V-VI), and by number of injections.

**10. Original text and location**

Listing 16.2.7.1 – Adverse Events

Site- Subject	Analyses	System Organ Class// Verbatim Term	Preferred Term//	Start Date [Day #]	Stop Date [Day #]	Severity	Causality	Action Taken 	Out 	Serious?
Treatment: Revanesse Ultra										
...										
...										
...										
Treatment: Revanesse Ultra+										
...										
...										
...										
Treatment: Unidentified (not on face)										
...										
...										

Analyses: I = Intent-to-Treat (ITT) Analyses only, M = Modified Intent-to-Treat (MITT) and ITT Analyses, P = Per-Protocol, MITT, and ITT Analyses.

Day # is calculated from baseline (Visit 1) date. Day 1 is the baseline date while Day -1 is the day prior to the baseline visit.

 Action Taken: 1=None, 2=Study treatment interrupted/discontinued, 3=Non-drug therapy, 4=New OTC or Rx drug added, 4=Hospitalized

 Out (outcome): 1= Resolved, 2=Improved, 3=Stabilized, 4=Worsened, 5=Unchanged, 6=Lost to Follow-up/Unknown, 7=Fatal

O:\Studies\ Prolenium\SYM 2016-02\Biometrics\Programs\Listing\xxx.sas ran on Month Day Year at hh:mm on data from Month Day, Year.

**Revised text and location**

Listing 16.2.7.1 – Adverse Events

Site-Subject	Analy	Skin Type	AE Reported by	System Organ Class// Preferred Term// Verbatim Term	Start Date [Day #]	Stop Date [Day #]	Severity	Causality	Action Taken 	Out 	Serious?
Treatment: Revanesse Ultra											
...											
...											
...											
Treatment: Revanesse Ultra+											
...											
...											
...											
Treatment: Unidentified (not on face)											
...											
...											

Analy (Analyses): I = Intent-to-Treat (ITT) Analyses only, M = Modified Intent-to-Treat (MITT) and ITT Analyses, P = Per-Protocol, MITT, and ITT Analyses.

Day # is calculated from baseline (Visit 1) date. Day 1 is the baseline date while Day -1 is the day prior to the baseline visit.

 Action Taken: 1=None, 2=Study treatment interrupted/discontinued, 3=Non-drug therapy, 4=New OTC or Rx drug added, 4=Hospitalized

 Out (outcome): 1= Resolved, 2=Improved, 3=Stabilized, 4=Worsened, 5=Unchanged, 6=Lost to Follow-up/Unknown, 7=Fatal

O:\Studies\ Prollenium\SYM 2016-02\Biometrics\Programs\Listing\xxx.sas ran on Month Day Year at hh:mm on data from Month Day, Year.

**Reason for the amendment**

To add “Skin Type” and “AE Reported by” which will help refer to the appropriate AE records when reviewing the newly added summary tables.

**11. Original text and location**

***Note:***

Repeat Listing 16.2.7.1 for AEs that led to study treatment interrupted/Discontinued and Serious AEs –

Listing 16.2.7.2 – Adverse Events Leading to Study Treatment Interrupted/Discontinued

Listing 16.2.7.3 – Serious Adverse Events

**Revised text and location**

***Note:***

Repeat Listing 16.2.7.1 for AEs that led to study treatment interrupted/Discontinued and Serious AEs –

Listing 16.2.7.2 – Adverse Events Leading to Study Treatment Interrupted/Discontinued

Listing 16.2.7.3 – Serious Adverse Events

**Listing 16.2.7.4 – Injection Site Adverse Events Lasted More Than 30 Days**

**Reason for the amendment**

To add Listing 16.2.7.4 per Sponsor request

## **12. Newly added summary table and data listings for the 17 subjects who rolled over from SYM 2014-02 into SYM 2016-02**

### Subject Subgroup Summary Tables

- 1) Subgroup Table s14.1.1 – Analysis Population for Subset of Rollover subjects
- 2) Subgroup Table s14.1.2 – Subject Discontinuations by Reason for Subset of Rollover Subjects
- 3) Subgroup Table s14.1.3 – Subject Enrollment by Study Site for Subset of Rollover Subjects
- 4) Subgroup Table s14.1.4 – Significant Protocol Violations for Subset of Rollover Subjects
- 5) Subgroup Table s14.1.5.1 – Demographic and Baseline Characteristics for Intent-to-Treat Population - Subset of Rollover Subjects
- 6) Subgroup Table s14.1.5.2 - Demographic and Baseline Characteristics for Modified Intent-to-Treat Population - Subset of Rollover Subjects
- 7) Subgroup Table s14.1.5.3 - Demographic and Baseline Characteristics for Per-Protocol Population - Subset of Rollover Subjects
- 8) Subgroup Table s14.1.5.4 – Key Demographic and Baseline Characteristics by Site for Intent-to-Treat Population - Subset of Rollover Subjects
- 9) Subgroup Table s14.1.5.5 – Summary of Racial Distribution within Fitzpatrick Skin Type for Intent-to-Treat Population - Subset of Rollover Subjects
- 10) Subgroup Table s14.2.1.1 – Primary Efficacy: Proportion of Responders Immediately After Injection at Visit 1/Day 1 for Subset of Rollover Subjects
- 11) Subgroup Table s14.2.1.2 – Primary Efficacy by Study Site: Proportion of Responders Immediately After Injection at Visit 1/Day 1 for Subset of Rollover Subjects
- 12) Subgroup Table s14.2.2.4 – Secondary Efficacy: Proportion of Responders at 60 Minutes Post Injection at Visit 1/Day 1 for Subset of Rollover Subjects
- 13) Subgroup Table s14.2.2.5 – Secondary Efficacy: Proportion of Responders at 2 Weeks Post Injection at Visit 2/Week 2 for Subset of Rollover Subjects
- 14) Subgroup Table s14.2.3.1 – Other Efficacy: Wrinkle Severity Rating Scale (WSRS) by Visit for Modified Intent-to-Treat Population - Subset of Rollover Subjects
- 15) Subgroup Table s14.2.3.2 – Other Efficacy: Wrinkle Severity Rating Scale (WSRS) by Visit for Per-Protocol Population - Subset of Rollover Subjects
- 16) Subgroup Table s14.2.4.1 – Other Efficacy: Patient Global Aesthetic Improvement (pGAI) by Visit for Modified Intent-to-Treat Population - Subset of Rollover Subjects

- 17) Subgroup Table s14.2.4.2 – Other Efficacy: Patient Global Aesthetic Improvement (pGAI) by Visit for Per-Protocol Population - Subset of Rollover Subjects
- 18) Subgroup Table s14.2.5.1 – Other Efficacy: Investigator Global Aesthetic Improvement (iGAI) by Visit for Modified Intent-to-Treat Population - Subset of Rollover Subjects
- 19) Subgroup Table s14.2.5.2 – Other Efficacy: Investigator Global Aesthetic Improvement (iGAI) by Visit for Per-Protocol Population - Subset of Rollover Subjects
- 20) Subgroup Table s14.3.1 – Exposure to Study Product, Investigator Ease of Use Assessment and Patient Comfort Rating for Intent-to-Treat Population - Subset of Rollover Subjects
- 21) Subgroup Table s14.3.2.1 – Injection Site Treatment-Emergent Adverse Events (TEAEs) by MedDRA System Organ Class and Preferred Term for Intent-to-Treat Population – Subset of Rollover Subjects  
 (Note:  
 Breakdown of previous injections for all injection site TEAEs through Tables s14.3.2.5, s14.3.2.5a and s14.3.2.5.  
 Breakdown of severity for all injection site TEAEs through Table s14.3.2.2.  
 Breakdown of duration, as planned for most frequently occurring injection site TEAEs, through Table s14.3.2.8)
- 22) Subgroup Table s14.3.2.2 – Injection Site Treatment-Emergent Adverse Events (TEAEs) by MedDRA System Organ Class, Preferred Term, and Severity for Intent-to-Treat Population - Subset of Rollover Subjects
- 23) Subgroup Table s14.3.2.3 – Most Frequently Occurring Injection Site Treatment-Emergent Adverse Events (TEAEs) by MedDRA Preferred Term for Intent-to-Treat Population - Subset of Rollover Subjects
- 24) Subgroup Table s14.3.2.4 – Injection Site Treatment-Emergent Adverse Events (TEAEs) by MedDRA System Organ Class, Preferred Term, and Fitzpatrick Skin Type (FST) for Intent-to-Treat Population - Subset of Rollover Subjects
- 25) Subgroup Table s14.3.2.5 – Injection Site Treatment-Emergent Adverse Events (TEAEs) by MedDRA System Organ Class, Preferred Term, and Number of Injection for Intent-to-Treat Population - Subset of Rollover Subjects
- 26) Subgroup Table s14.3.2.5a – Injection Site Treatment-Emergent Adverse Events (TEAEs) Reported by Subject by MedDRA System Organ Class, Preferred Term, and Number of Injection for Intent-to-Treat Population - Subset of Rollover Subjects
- 27) Subgroup Table s14.3.2.5b – Injection Site Treatment-Emergent Adverse Events (TEAEs) Reported by Investigator by MedDRA System Organ Class, Preferred Term, and Number of Injection for Intent-to-Treat Population - Subset of Rollover Subjects
- 28) Subgroup Table s14.3.2.6 – Overall Summary of Injection Site Treatment-Emergent Adverse Events (TEAEs) for Intent-to-Treat Population - Subset of Rollover Subjects
- 29) Subgroup Table s14.3.2.7 – Severity of Most Frequently Occurring Injection Site Treatment-Emergent Adverse Events (TEAEs) by MedDRA Preferred Term for Intent-to-Treat Population - Subset of Rollover Subjects

- 30) Subgroup Table s14.3.2.8 – Duration of Most Frequently Occurring Injection Site Treatment-Emergent Adverse Events (TEAEs) by MedDRA Preferred Term for Intent-to-Treat Population - Subset of Rollover Subjects
- 31) Subgroup Table s14.3.3.2 – Non-Injection Site Treatment-Emergent Adverse Events (TEAEs) by MedDRA System Organ Class, Preferred Term, and Severity for Intent-to-Treat Population - Subset of Rollover Subjects
- 32) Subgroup Table s14.3.3.3 – Most Frequently Occurring Non-Injection Site Treatment-Emergent Adverse Events (TEAEs) by MedDRA Preferred Term for Intent-to-Treat Population - Subset of Rollover Subjects
- 33) Subgroup Table s14.3.3.4 – Non-Injection Site Treatment-Emergent Adverse Events (TEAEs) by MedDRA System Organ Class, Preferred Term, and Causality for Intent-to-Treat Population - Subset of Rollover Subjects
- 34) Subgroup Table s14.3.3.5 – Non-Injection Site Treatment-Emergent Adverse Events (TEAEs) by MedDRA System Organ Class, Preferred Term, and Fitzpatrick Skin Type (FST) for Intent-to-Treat Population - Subset of Rollover Subjects
- 35) Subgroup Table s14.3.3.6 – Non-Injection Site Treatment-Emergent Adverse Events (TEAEs) by MedDRA System Organ Class, Preferred Term, and Number of Injection for Intent-to-Treat Population - Subset of Rollover Subjects

#### Subject Subgroup Listings

- 1) Subgroup Listing s16.2.1.1 – Subject Analysis Status for Subset of Rollover Subjects
- 2) Subgroup Listing s16.2.1.2 – Subject Disposition for Subset of Rollover Subjects
- 3) Subgroup Listing s16.2.2.3 – Significant Protocol Violations for Subset of Rollover Subjects
- 4) Subgroup Listing s16.2.2.4 – Comments for Subset of Rollover Subjects
- 5) Subgroup Listing s16.2.4.1 – Demographics for Subset of Rollover Subjects
- 6) Subgroup Listing s16.2.4.3 – Medical History Findings for Subset of Rollover Subjects
- 7) Subgroup Listing s16.2.5.1 – Treatment Administration at Visit 1/Day 1 for Subset of Rollover Subjects
- 8) Subgroup Listing s16.2.5.2 – Touch-Up Treatment Administration at Visit 2/Week 2 for Subset of Rollover Subjects
- 9) Subgroup Listing s16.2.6.1.1 – Efficacy Evaluations of Visual Analog Scale (VAS) for Pain for Subset of Rollover Subjects
- 10) Subgroup Listing s16.2.6.1.2 – Efficacy Evaluations (WSRS, pGAI, iGAI) for Subset of Rollover Subjects
- 11) Subgroup Listing s16.2.6.2.1 – Primary and Secondary Efficacy Responses for Modified Intent-to-Treat Population - Subset of Rollover Subjects
- 12) Subgroup Listing s16.2.6.2.2 – Other Efficacy Responses for Modified Intent-to-Treat Population - Subset of Rollover Subjects
- 13) Subgroup Listing s16.2.6.3.1 – Primary and Secondary Efficacy Responses for Per-Protocol Population - Subset of Rollover Subjects
- 14) Subgroup Listing s16.2.6.3.2 – Other Efficacy Responses for Per-Protocol Population - Subset of Rollover Subjects

- 15) Subgroup Listing s16.2.7.1 – Adverse Events for Subset of Rollover Subjects
- 16) Subgroup Listing s16.2.7.2 – Adverse Events Leading to Study Treatment Interrupted/Discontinued for Subset of Rollover Subjects
- 17) Subgroup Listing s16.2.7.3 – Serious Adverse Events for Subset of Rollover Subjects

**Reason for the amendment**

To add TLs for the subject of rollover subjects per Sponsor request

## Statistical Analysis Plan

### 1 Purpose of Statistical Analysis Plan

The purpose of the statistical analysis plan is to describe in detail all the data, statistical methods, and summary tables required to implement the statistical analysis of Clinical Study Protocol SYM 2016-02 (Section 9 in the study protocol version 1.0, dated July 08, 2016).

### 2 Study Objectives

To compare the safety and efficacy profiles of Revanesse® Ultra + (with lidocaine, hereafter referred to as Revanesse Ultra +) to Revanesse Ultra for subjects undergoing correction of nasolabial folds (NLFs).

### 3 Study Design and Sample Size Determination

#### 3.1 Study Design

For the purpose of exploring the above objectives, the study will be conducted as a multicenter, double-blind, randomized, split-face study in subjects seeking nasolabial fold correction. Subjects will be treated with Revanesse Ultra + in the NLF on one side of the face and Revanesse Ultra in the NLF on the other side of the face. The side of the face for each study product will be randomly assigned. The investigator and the subject will be blinded to the treatment; injections of the study product will be performed by an unblinded injecting investigator.

At each visit, investigator and subject evaluations of the treated areas will be performed and recorded. Visits will occur at:

Visit 1/Week 0 (Day 1) – baseline and treatment

Visit 2/Week 2 – interim visit, touch-up if the iGAI score = 3 or 4

Visit 3/Week 4 – interim visit

Visit 4/Week 12 – interim visit

Visit 5/ Week 24 –End of Study

Evaluations include:

Pain assessment using a visual analog scale (VAS)

Wrinkle Severity Rating Scale (WSRS)

Patient Global Aesthetic Improvement (pGAI)

Investigator Global Aesthetic Improvement (iGAI)

Safety will be assessed by monitoring adverse events (AEs) at all study visits.

Other evaluations include Investigator Ease of Use Assessment.

#### 3.2 Sample Size Determination

Restylane-L Injectable Gel was approved in supplement P040024/S039 on January 29, 2010 for mid-to-deep dermal implantation for the correction of moderate to severe facial wrinkles and folds such as NLFs. For the supplement study (MA-1100-001), the primary endpoint was the proportion of subjects who had a within-subject difference in VAS (Restylane minus Restylane-L) pain assessment of at least 10 mm at injection. The objective was to show that the 95% confidence interval for the within-subject difference lay above 50%. The key study results are shown in Table 1 (Source: Summary of Safety and Effectiveness Data (SSED), for Restylane-L Injectable Gel).

Table 1 Subjects with at Least a 10 mm Difference in VAS (*Restylane – Restylane-L*)

Timepoint	No. of subjects with assessments**	Number of subjects with $\Delta \geq 10$ mm			
		n	%	95% LCL	95% UCL
Treatment	60	43	71.7	58.6	82.5
15 Minutes	60	28	46.7	33.7	60.0
30 Minutes	60	17	28.3	17.5	41.4
45 Minutes	60	10	16.7	8.3	28.5
60 Minutes	60	4	6.7	1.8	16.2

Source: Statistical Report: Appendix 16.1.9, Table 1.23, Appendix 16.2.6.1

\*Primary endpoint

\*\*Denominator (N), % = 100\*n/N

UCL=upper confidence limit; LCL=lower confidence limit

The following sample size is calculated based on the data from the above Restylane-L study, assuming that similar statistics and the same criterion will be applicable for Revanesse Ultra + vs Revanesse Ultra.

Table 2 Sample Size Calculations

Proportion of Responders	Power by N (Number of mITT subjects)	
	N=90	N=80
70%	97.2%	94.1%
68%	93.3%	87.8%

To detect the difference between the null hypothesis proportion of responders of 50% and the alternative proportion of responders of 70% via a two-sided exact binomial test with a 0.05 significance level, 80 mITT subjects will supply a power of 94.1%. For the alternative proportion of responders of 68%, 80 mITT subjects will supply a power of 87.8%.

A total of 100 subjects will be randomized to obtain 80 mITT subjects and to provide adequate data for monitoring safety of the study product.

#### 4 Populations To Be Analyzed

Three subject populations are defined as follows:

- (1) Intent-to-treat (ITT) (safety population): All randomized subjects who received study product.
- (2) Modified intent-to-treat (mITT): All randomized subjects who met the inclusion/exclusion criteria, were randomized, received both study products, and returned for at least 1 post-injection assessment of pain score immediately post injection from both sides of the face.
- (3) Per-protocol (PP): All randomized subjects who met all inclusion/exclusion criteria; received both study products; completed Visit 5/Week 24 within the specified window; had data on pain score from both sides of the face immediately post injection and at 15, 30, 45, and 60 minutes post injection at Visit 1/Day1; had data on pain score at 2 weeks post injection (prior to touch-up); and had no significant protocol violations that would affect the treatment evaluation.

For the purpose of determining the PP status of the subject, “significant protocol violations” are any unforeseen events that occurred during the conduct of the trial that result in noteworthy study protocol violations that could have possibly interfered with the therapeutic administration of the treatment or the precise evaluation of treatment efficacy.

Efficacy analyses will be performed on the mITT and PP populations. Analyses of safety and other evaluations will be performed on the ITT population.

## 5 Planned Analyses

### 5.1 Methodological Considerations

SAS software (version 9.1.3 or higher) will be used for all data analyses and tabulations.

Two-sided hypothesis testing will be conducted for all inferential analyses. Resulting p-values less than 0.05 will be considered statistically significant. To control the overall error rate, a hierarchical approach will be applied. Upon the significance of the primary efficacy outcome, secondary endpoints will be analyzed sequentially. If success is achieved at 15 minutes, 30 minutes will be evaluated; if success is achieved at 30 minutes, 45 minutes will be evaluated; if success is achieved at 45 minutes, 60 minutes will be evaluated; and if success is achieved at 60 minutes, 2 weeks post-injection will be evaluated.

All the data points will be presented in [subject data listings](#).

### 5.2 Handling of Dropouts or Missing Data

For demographics, baseline characteristics, safety profile and other evaluations, each variable will be analyzed using the existing data. Subjects with missing data will be excluded only from the analyses for which data are not available.

There will not be missing data for the primary efficacy endpoint for the mITT and PP based on the definitions of these analysis populations ([Section 4](#)).

For the mITT analysis of the secondary efficacy endpoints, missing VAS scores will be replaced using the multiple imputation (MI) approach. Depending on the pattern of missingness, a two-step process may be employed. If missing data occur for an intermediate visit or time point, they will be imputed first via a Markov Chain Monte Carlo (MCMC) method. As a result, a monotone missingness pattern will be obtained for the data to be fully imputed. The subsequent imputation will use Monotone Regression to produce 5 imputed datasets where the remaining missing data are filled in using 5 different sets of values. The average value of the 5 copies of the VAS scores from MI will be used for each missing data point in the mITT analysis.

To prepare for MI, for subjects who are early discontinued from the study, their VAS scores captured at the termination visit will be assigned to the nearest corresponding scheduled visit. VAS scores to be imputed include those at 15, 30, 45, and 60 minutes post injection and at 2 weeks post injection (prior to touch-up). Other variables that go into the imputation models include treatment, site, and key baseline characteristics such as age, gender, race and Fitzpatrick skin type. When missing VAS score at a given visit or time point is imputed, the values from all its previous visits or time points will be included as predictor in the imputation

model. For example, for a subject with missing VAS at 45 minutes post injection on Day 1, the VAS scores from immediately after injection, 15 minutes and 30 minutes post injection for the subjects will be included in the imputation model.

Other efficacy endpoints will be tabulated using the observed data; no missing values will be replaced in the analyses.

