#### 5.5.2 Secondary Efficacy Analysis

The secondary efficacy endpoints are the proportion of responders at 15, 30, 45, and 60 minutes post injection and at 2 weeks post injection (prior to touch-up). Similar method used for the primary efficacy endpoint will be used to analyze the secondary variables.

Missing VAS scores for the mITT analysis will be replaced using the multiple imputation (MI) method. To evaluate the robustness of MI method, subjects with missing VAS scores for the mITT analysis will also be considered in two different ways: (1) as non-responders to the test product (worst case scenario), and (2) as responders to the test product (best case scenario).

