**Note:**

Table 14.2.1.2 will be used as the shell for the following table:

Table s14.2.1.2 – Primary Efficacy by Study Site: Proportion of Responders Immediately After Injection at Visit 1/Day 1 for Subset of Rollover Subjects

Table 14.2.2.1 – Secondary Efficacy: Proportion of Responders at 15 Minutes Post Injection at Visit 1/Day 1

Population Endpoint	Statistics	Revanesse Ultra	Revanesse Ultra+	Difference: Ultra minus Ultra+
Modified Intent-to-Treat (mITT)				
VAS Score	N	0	0	0
	Mean ± SD	0.0 ± 0.00	0.0 ± 0.00	0.0 ± 0.00
	Median	0.0	0.0	0.0
	Min, Max	0, 0	0, 0	0, 0
Responders (MI)*	n (%)			0 (0.0%)
	95% Confidence Interval			(0.0%, 0.0%) 
Responders (WCS)*	n (%)			0 (0.0%)
	95% Confidence Interval			(0.0%, 0.0%) 
Responders (BCS)*	n (%)			0 (0.0%)
	95% Confidence Interval			(0.0%, 0.0%) 
Per-Protocol (PP)				
VAS Score	N	0	0	0
	Mean ± SD	0.0 ± 0.00	0.0 ± 0.00	0.0 ± 0.00
	Median	0.0	0.0	0.0
	Min, Max	0, 0	0, 0	0, 0
Responders	n (%)			0 (0.0%)
	95% Confidence Interval			(0.0%, 0.0%) 

Responder (to Revanesse Ultra+) is defined as a subject who had a within-subject difference (Revanesse Ultra minus Revanesse Ultra+) in VAS pain score of at least 10 mm on a 100-mm scale.

Missing VAS scores for the mITT analysis will be replaced using the multiple imputation (MI) method.

\*MI (Multiple Imputation): Subjects with missing VAS scores are defined as responder or non-responder based on their VAS values through MI; WCS (Worst Case Scenario): Subjects with missing VAS scores are considered non-responders; BCS (Best Case Scenario): Subjects with missing VAS scores are considered responders.

The 95% confidence intervals are constructed using a one-sample binomial exact test.

Source: [Listing 16.2.6.2.1](#), [16.2.6.3.1](#)

O:\Studies\Prollenium\SYM 2016-02\Biometrics\Programs\Tables\xxx.sas ran on Month Day, Year at hh:mm on data from Month, Day, Year.

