**Note:**

Table 14.2.2.1 will be used as the shell for the following tables:

Table 14.2.2.2 – Secondary Efficacy: Proportion of Responders at 30 Minutes Post Injection at Visit 1/Day 1

Table 14.2.2.3 – Secondary Efficacy: Proportion of Responders at 45 Minutes Post Injection at Visit 1/Day 1

Table 14.2.2.4 – Secondary Efficacy: Proportion of Responders at 60 Minutes Post Injection at Visit 1/Day 1

Table s14.2.2.4 – Secondary Efficacy: Proportion of Responders at 60 Minutes Post Injection at Visit 1/Day 1 for Subset of Rollover Subjects

Table 14.2.2.5 – Secondary Efficacy: Proportion of Responders at 2 Weeks Post Injection at Visit 2/Week 2

Table s14.2.2.5 – Secondary Efficacy: Proportion of Responders at 2 Weeks Post Injection at Visit 2/Week 2 for Subset of Rollover Subjects

Table 14.2.3.1 – Other Efficacy: Wrinkle Severity Rating Scale (WSRS) by Visit for Modified Intent-to-Treat Population

Study Visit	Category	Revanesse Ultra	Revanesse Ultra+	Difference: Ultra minus Ultra+
Visit 1/Day 1	N	0	0	
	1 = Absent	0 (0%)	0 (0%)	
	2 = Mild	0 (0%)	0 (0%)	
	3 = Moderate	0 (0%)	0 (0%)	
	4 = Severe	0 (0%)	0 (0%)	
	5 = Extreme	0 (0%)	0 (0%)	
	N of subjects with data from both sides			0
	Mean ± SD			0.0 ± 0.00
Visit 2/Week 2	...			
...	...			
...	...			
Visit 5/Week 24	N	0	0	0
	1 = Absent	0 (0%)	0 (0%)	
	2 = Mild	0 (0%)	0 (0%)	
	3 = Moderate	0 (0%)	0 (0%)	
	4 = Severe	0 (0%)	0 (0%)	
	5 = Extreme	0 (0%)	0 (0%)	
	N of subjects with data from both sides			0
	Mean ± SD			0.0 ± 0.00

Missing values are not imputed for the summary. A positive mean value in difference is in favor of Revanesse Ultra+.

Source: [Listing 16.2.6.2.1](#), [16.2.6.3.1](#)

O:\Studies\Prolenium\SYM 2016-02\Biometrics\Programs\Tables\xxx.sas ran on Month Day, Year at hh:mm on data from Month, Day, Year.

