**Note:**

Listing 16.2.6.1.2 will be used as the shell for the following listing:

Listing s16.2.6.1.2 – Efficacy Evaluations (WSRS, pGAI, iGAI) for Subset of Rollover Subjects

*(Programmer note for Listing s16.2.6.1.2: Add Fitzpatrick Skin Type to the listing and present the data sorted by skin type.)*

Listing 16.2.6.2.1 – Primary and Secondary Efficacy Responses for Modified Intent-to-Treat Population

Site-Subject	Study Visit	Time Point	Revanesse Ultra		Revanesse Ultra+		Ultra minus Ultra+ in VAS	Responder*				
			Observed or MI	VAS Score	Observed or MI	VAS Score		Observed	MI	WSC	BCS	
xx-xxxx	III	Visit 1/Day 1	Immediately after injection	Observed	50	Observed	42	8	No			
			15 minutes post injection	Observed	46	MI	34.4	11.6	Yes	No	Yes	
			30 minutes post injection	Observed	31	MI	25.5	5.5	No	No	Yes	

Missing VAS scores for the mITT analysis will be replaced using the multiple imputation (MI) method. The average values from the MI copies of VAS are present and used for analysis. \*Responder (to Revanese Ultra+) is defined as a subject who had a within-subject difference (Revanese Ultra minus Revanese Ultra+) in VAS pain score of at least 10 mm on a 100-mm scale. Observed: Subjects are defined as responder or non-responder based on the non-missing values; MI (Multiple Imputation): Subjects with missing VAS scores are defined as responder or non-responder based on their VAS values through MI; WCS (Worst Case Scenario): Subjects with missing VAS scores are considered non-responders; BCS (Best Case Scenario): Subjects with missing VAS scores are considered responders.  
O:\Studies\ Prolenium\SYM 2016-02\Biometrics\Programs\Listing\xxx.sas ran on Month Day Year at hh:mm on data from Month Day, Year.

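### For the mITT secondary endpoints the SAP averages five imputed VAS scores and classifies once, so the Responders (MI) interval treats imputed scores as observed; the effect is minor at up to about 10% missing

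*SAP*

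**What the plan says.** SAP 5.2 fills intermediate gaps by MCMC, then uses monotone regression to produce five imputed datasets. It ends with the averaging rule: "The average value of the 5 copies of the VAS scores from MI will be used for each missing data point". The footnote to Listing 16.2.6.2.1 confirms that this is the analysed value: "The average values from the MI copies of VAS are present and used for analysis". The sample rows of that listing show how it works. At 15 minutes an observed 46 on the Ultra side and an averaged 34.4 on the Ultra+ side give a difference of 11.6 and a single MI flag of Yes.

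Table 14.2.2.1 (15 minutes) has one count and percentage in its Responders (MI) row. Its footnotes say "Subjects with missing VAS scores are defined as responder or non-responder based on their VAS values through MI" and "The 95% confidence intervals are constructed using a one-sample binomial exact test". The note after the table says "Table 14.2.2.1 will be used as the shell for the following tables", which extends the layout to 30, 45 and 60 minutes, to 2 weeks, and to two rollover tables. SAP 5.5.2 adds "Similar method used for the primary efficacy endpoint will be used to analyze the secondary variables", so success again means a lower 95% bound above 50%.

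The worst-case and best-case rows enter as a check on the MI row: "To evaluate the robustness of MI method, subjects with missing VAS scores for the mITT analysis will also be considered in two different ways". No section plans an analysis within each imputed dataset or a pooled variance.

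**The concern.** Multiple imputation carries the uncertainty about a missing value through the spread of results across datasets. Here the five draws collapse to one number before any analysis. The subject in the sample listing lies 1.6 mm above the cut-off. Individual draws could well fall on both sides of 10 mm, yet the subject counts as a certain responder. The exact interval then credits the analysis with N fully observed subjects.

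The MI row is the reference row for the mITT secondary endpoints, since the other two rows test its robustness. An interval that is too narrow there could overstate precision at five time points. It could also affect the fixed sequence in SAP 5.1, which begins "If success is achieved at 15 minutes, 30 minutes will be evaluated".

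**Working it through.** **1. The plan's own figures.** SAP 3.2 gives N = 80 mITT subjects and a two-sided exact test at 0.05. The Clopper-Pearson lower bound is 0.497 at 49/80 and 0.510 at 50/80, so success needs at least 50. P(X ≥ 50) is 94.1% at 70% and 87.9% at 68%; SAP Table 2 gives 94.1% and 87.8%. The one-sided error at a true 50% is 1.65%.

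**2. Effect of averaging on the proportion.** Assume normal within-subject differences and a share R² of their variance predicted by earlier data. A single draw has standardised variance 1. The mean of five draws has variance R² + (1 − R²)/5. With z = Φ⁻¹(p) and a fraction f missing,

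bias ≈ f × [Φ(z / √(R² + (1 − R²)/5)) − p].

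- p = 0.65, R² = 0.2, f = 0.2: z = 0.385 and √(0.2 + 0.16) = 0.6, so Φ(0.642) = 0.740. The bias is 0.2 × 0.090 = +1.8 points.
- Same p and f, R² = 0.7: √0.76 = 0.872, so Φ(0.442) = 0.671 and the bias is +0.4 points.
- p = 0.283, R² = 0.2, f = 0.2: z = −0.574, so Φ(−0.957) = 0.169 and the bias is about −2.3 points.

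Simulation gives +0.4 to +1.8 points at 65% and −2.0 to −0.6 at 28.3%. At 5% missing the bias is at most about 0.5 points.

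**3. Effect on the interval.** Let W be the mean within-dataset variance p(1 − p)/N and B the variance of the five proportions. Rubin's total variance is T = W + (1 + 1/5)B, and the effective sample size is N × W/T. Assumptions: N = 80, SD 25 mm, missing completely at random, regression imputation, R² of 0.2, 0.5 and 0.7, and 8,000 trials per cell. The simulation standard error is about 0.5 points near 75% (√(0.75 × 0.25/8,000)). Ranges run over R².

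| Missing | Effective n at true 50% (SAP uses 80) | SAP false success at true 50% | SAP coverage, true rates 6.7–65% | Success at true 65%: SAP / pooled |
|---|---|---|---|---|
| 5% | 76.0–77.6 | 1.5–2.3% | 94.4–98.5% | 72.5–73.7% / 71.4–73.0% |
| 10% | 72.2–75.3 | 2.0–2.5% | 93.2–98.3% | 72.4–75.9% / 69.7–71.6% |
| 20% | 65.6–71.0 | 2.3–3.7% | 90.3–98.1% | 73.7–78.7% / 65.0–69.3% |

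With complete data, success at a true 65% is 72.4%. At 20% missing the SAP rule therefore succeeds more often than if every score had been observed. If earlier scores predict nothing (R² = 0), false success reaches 3.3% at 10% missing and 4.8% at 20%, with coverage of 93.6% and 90.3% at a true 50%.

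**4. Scores bounded at 0 and 100.** In 48 cells with 20% missing and true rates of 13 to 48%, SAP bias is −1.9 to +0.7 points and pooled bias −0.2 to +1.4. The SAP rule is the less biased in 21 cells. Its coverage is 88.7–95.0%, against 95.7–97.3% with pooling and the effective-n interval. Coverage is the consistent weakness; the direction of bias is not.

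**5. Reach through the gate.** The reference study in SAP 3.2 shows 46.7% responders at 15 minutes and 28.3% at 30. With complete data P(X ≥ 50) is 0.3% and 2 × 10⁻¹⁰. On that benchmark the sequence almost always stops at 15 minutes.

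**The case against.** The strongest reply is that almost no decision turns on this. mITT membership requires the immediate scores from both sides (SAP 4), and four of the five secondary scores follow within 60 minutes, so few should be missing. The worst-case and best-case rows carry their own exact intervals, so a result that depends on imputation would be visible. The PP row needs no imputation. On the benchmark rates the gate closes at once. All this stands and keeps the point minor. Low missingness is still an inference: the visit list in protocol 8.7.1 omits the 45-minute score that 8.6.7 and the flow chart require. The bounding rows also do not give the MI row a valid interval.

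A second reply is that pooling alone is not clearly better. SAP 5.2 lists treatment as an imputation covariate, which points to one record per side, and it does not name the opposite side's score as a predictor. Under that model, with an assumed between-side correlation of 0.7 and 20% missing, pooling gave a bias of +2.0 points at a true 6.7% (SAP rule −0.5) and only 57.7% success at a true 65%. At an assumed correlation of 0.3, pooling was the less biased in most cells. This objection stands, and it is why the fix below also changes the imputation model.

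A third reply is that an exact interval at a non-integer effective n is not routine MI code. That is fair, but it is a short addition.

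**Conclusion.** The plan is wrong as written on this point, and the point is minor. The text establishes single imputation of an averaged score, one classification, and an interval that omits between-imputation variance. At up to about 10% missing, the conservatism of the exact interval absorbs most of the effect. At about 20%, with weak prediction, false success and coverage move visibly. These sizes rest on assumed missing rates, distributions and imputation models, because the documents supply none of them.

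A reader might infer more than the documents support:
- *That averaging favours the test product.* Under normality it pushes rates away from 50%. At the benchmark rates from 15 minutes on, all below 50%, that is downward. With bounded scores even this direction is not general.
- *That the main claim is at risk.* By definition the mITT and PP populations have no missing primary score, and PP also requires every secondary score.
- *That a gated secondary claim is likely to be false.* That would need a 15-minute rate far above the benchmark; the 65% used here is an assumption.

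**What to change.** Impute the two sides jointly: one record per subject, with earlier scores from both sides and any observed opposite-side score as predictors. In each of the five datasets derive the within-subject difference and responder status, then pool the proportions by Rubin's rules. Report an interval that reduces to the planned exact one when nothing is missing, for example Clopper-Pearson at the Rubin effective sample size, using N itself if nothing is missing or the total variance is zero.

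The success bar is then a pooled proportion of 0.617 at effective n 78, 0.622 at 72 and 0.628 at 66, against 50/80 = 0.625 with complete data. The first is below 0.625 only because a pooled count need not be an integer; simulated false success stays at 1.3–1.9%. A plain t interval is not a good substitute: it covers 90.4–93.0% at a true 6.7% and would pass 49/80.

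Text to edit:
- SAP 5.2: the averaging sentence and the imputation-model description.
- SAP 5.5.2: the sentence that carries over the primary method.
- Table 14.2.2.1: the MI row, responder footnote and interval footnote, which carry to Tables 14.2.2.2–14.2.2.5, s14.2.2.4 and s14.2.2.5.
- Listing 16.2.6.2.1: the footnote and the MI responder column, which should show how many of the five imputations class the subject as a responder.

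Keep the worst-case and best-case rows. No new data are needed. The interval at a true 50% widens from about 0.227 to 0.230–0.233 at 5% missing, 0.234–0.239 at 10% and 0.241–0.252 at 20%. At a true 65% with 20% missing, the chance of success falls from about 74–79% to about 65–69% with joint imputation, and to about 58–65% if the sides stay as separate records.
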